4.10.3 Tertiary Efficacy Analyses

As tertiary efficacy analysis adaptive speech in noise [speech-to-noise ratio, 50% speech understanding] with a current hearing aid (if used by the patient) will be presented. Summarization will be made for the ITT population totally and by SSD and Mixed/Conductive (if sufficient data is collected).

4.11 Safety Analyses

The primary safety analysis will be evaluated at 6 months.

4.11.1 Implant site evaluation

Evaluation about numbness will be presented by visit. Changes from first measurement may be evaluated.

4.11.2 Adverse Events

AEs will be included in the summaries for safety population.

A summary of subjects reporting at least one of the following AEs will be presented in an overview table:

- Any AE
- Any SAE
- Any Adverse Device Effect (ADE)
- Any Serious Adverse Device Effect (SADE)
- Any AESI

Summaries by CTCAE term presenting n (%) of AEs and n (%) of subjects with at least one AE will be provided for:

- All AE
- All SAE
- All Adverse Device Effect (ADE)
- All Serious Adverse Device Effect (SADE)
- All AESI

4.11.3 Device deficiency

Device deficiency will be presented by visit.

STATISTISKA KONSULTGRUPPEN		Statistical Analysis Plan	
Protocol: Clinical performance of a new implant system for bone conduction hearing		Protocol No: CBAS5539	
		Version: 1.0	Page 19 of 22

4.11.4 Audiogram

Audiogram (Air and Bone conduction), test side for 250, 500, 750, 1000, 1500, 2000, 3000, 4000, 6000 and 8000 Hz by SSD and Conductive/Mixed patients will be presented at visit 1, 6 and 8. At visit 6 and 8 is only bone conduction performed.

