3.3.4 Audiogram

Audiogram at Visit 1, Air condition/Bone conduction, Right/Left (transferred to test side/Non test side), Unmasked/Masked for 250, 500, 750, 1000, 1500, 2000, 3000, 4000, 6000 and 8000 Hz. At 3 months visit and 12 months visit test side audiogram, bone conduction (unmasked and if needed masked) thresholds at 250, 500, 750, 1000, 1500, 2000, 3000, 4000 and 6000Hz will be collected.

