4.2 Timing of analyses

The main efficacy analysis is made at 3 months and another follow-up analysis at 12 months. The primary Safety analysis will be made at 6 months.

- When locking the data at 3 months both efficacy and safety will be evaluated.
- When locking the data at 6 months only safety will be evaluated.
- When locking the data at 12 months both efficacy and safety will be evaluated.

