6 CHANGES OF ANALYSIS FROM PROTOCOL

No changes of the analyses according to the protocol are made.

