7 LISTING OF TABLE, FIGURES AND LISTINGS

7.1 Listing of Tables

Table 14.1.1	Patient Disposition and Data Sets Analysed
Table 14.1.2	Protocol Deviations Leading to Exclusion from PP Population (ITT Population)
Table 14.1.3.1	Demographics and Baseline Characteristics (ITT Population)
Table 14.1.3.2	Demographics and Baseline Characteristics (PP Population)
Table 14.1.4.1	Pre operation (ITT Population)
Table 14.1.4.2	Pre operation (PP Population)
Table 14.1.5.1	Audiogram (air) at visit 1, 6 and 8 - SSD patients (Safety Population)
Table 14.1.5.2	Audiogram (bone) at visit 1, 6 and 8 - SSD patients (Safety Population)
Table 14.1.5.3	Audiogram (air) at visit 1, 6 and 8 - conductive patients (Safety Population)
Table 14.1.5.4	Audiogram (bone) at visit 1, 6 and 8 - conductive patients (Safety Population)
Table 14.1.6	Medical History (ITT Population)
Table 14.1.7	Surgical History (ITT Population)
Table 14.1.8.1	Prior Medications (ITT population)
Table 14.1.8.2	Concomitant Medications (ITT population)
Table 14.1.9	Listing of Concomitant Treatments/Procedures (ITT population)
Table 14.2.1.1	Threshold Audiometry - Free field ATB System vs Unaided (ITT Population)
Table 14.2.1.2	Threshold Audiometry - Free field ATB System vs Unaided (PP Population)
Table 14.2.2.1	Adaptive speech recognition in noise and Speech in quiet ATB System vs Unaided (ITT Population)
Table 14.2.2.2	Adaptive speech recognition in noise and Speech in quiet ATB vs Unaided (PP Population)
Table 14.2.3.1	BC Direct (ITT Population)
Table 14.2.3.2	BC Direct (PP Population)
Table 14.2.4.1	HUI (ITT Population)
Table 14.2.4.2	HUI (PP Population)
Table 14.2.5.1	APHAB (ITT Population)
Table 14.2.5.2	APHAB (PP Population)
Table 14.2.6.1	The Speech, Spatial and Qualities of Hearing Scale (SSQ) (ITT Population)
Table 14.2.6.2	The Speech, Spatial and Qualities of Hearing Scale (SSQ) (PP Population)
Table 14.2.7.1	Surgery (ITT population)
Table 14.2.7.2	Surgery (PP population)
Table 14.2.8.1	Magnet strength (ITT population)
Table 14.2.8.2	Magnet strength (PP population)
Table 14.2.9.1	Daily use and soft-pad use (ITT population)

Protocol: Clinical performance of a new implant system for bone conduction hearing	Protocol No: CBAS5539	
	Version: 1.0	Page 21 of 22

- Table 14.2.9.2 Daily use and soft-pad use (PP population)
- Table 14.2.10.1 Threshold Audiometry - Free field ATB System vs Unaided (SSD patients ITT Population)

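### The SAP plans no summary of the 6-month bone-conduction audiogram (Visit 7), although 6 months is the time point of the primary safety analysis

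*SAP*

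**What the plan says.** **Protocol.** The safety objectives (Synopsis and section 4.3) list the audiogram as an outcome, with bone-conduction thresholds before surgery and at 3, 6 and 12 months. Sections 5.5 and 6.1 and the flow chart in section 8 schedule the test at Visits 6, 7 and 8. Section 6.1 identifies Visit 7 as the 6-month visit. Section 10.2.3 includes the audiogram among the safety variables. Section 4.3 and section 10.3.3 set the primary safety analysis at 6 months.

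**SAP, timing.** Section 4.11 states: "The primary safety analysis will be evaluated at 6 months". Section 4.2 adds: "When locking the data at 6 months only safety will be evaluated".

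**SAP, audiogram.** The variable definition in section 3.3.4 reads, for the post-operative measurements, "At 3 months visit and 12 months visit test side audiogram, bone conduction". Section 4.11.4 says the audiogram "by SSD and Conductive/Mixed patients will be presented at visit 1, 6 and 8" and continues: "At visit 6 and 8 is only bone conduction performed". In section 7.1, Table 14.1.5.2 is titled "Audiogram (bone) at visit 1, 6 and 8 - SSD patients (Safety Population)" and Table 14.1.5.4 "Audiogram (bone) at visit 1, 6 and 8 - conductive patients (Safety Population)". Section 1.1 says only that thresholds are taken before and after surgery, without naming months.

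**SAP, changes.** Section 6 states: "No changes of the analyses according to the protocol are made".

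**The concern.** The visit left out is the one at which the primary safety analysis is made. The SAP sets aside a data lock at 6 months for safety alone, yet its audiogram rule gives that lock nothing from the 6-month visit. A reader of the 6-month safety report would see bone-conduction thresholds from Visit 1 and Visit 6 only. The omission would not be repaired at 12 months, because the planned tables go from Visit 6 to Visit 8.

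At stake is a descriptive safety result: how unaided bone-conduction thresholds in the implanted ear are distributed 6 months after surgery, and how far they have moved from baseline. Large individual shifts have another route into the report, through adverse events. A modest shift across the group does not.

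**Working it through.** The documents state no figure to reproduce. The check compares time points, followed by simple counts.

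**1. Visits side by side (post-operative bone conduction)**

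| Source | Visit 6 (3 months) | Visit 7 (6 months) | Visit 8 (12 months) |
|---|---|---|---|
| Protocol Synopsis, 4.3 | yes | yes | yes |
| Protocol 5.5, 6.1, 8 | yes | yes | yes |
| SAP 3.3.4 | yes | no | yes |
| SAP 4.11.4, both sentences | yes | no | yes |
| SAP Tables 14.1.5.2 and 14.1.5.4 | yes | no | yes |

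Scheduled: 3. Planned for summary: 2. Not summarised: 3 − 2 = 1 of 3, namely Visit 7.

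In thresholds, the ceiling is 50 subjects × 9 frequencies × 3 visits = 1,350 scheduled unmasked values, of which 50 × 9 × 1 = 450 fall at Visit 7 (one study ear, no drop-out). This only restates the one in three. The values would still be measured; what is missing is their planned summary.

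**2. The other safety outcomes**

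The protocol has four safety outcomes. The SAP time points include 6 months for numbness (3.3.1) and device deficiency (3.3.3), and adverse events are covered from Visit 2 onward (3.3.2). That is 3 of 4. The audiogram is the only one without 6 months.

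**3. Age of the newest audiogram summary at the 6-month lock**

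Protocol 4.2 and SAP 3.2.2 treat the 3-month visit as week 12. The documents give no week number for the 6- and 12-month visits, so these are assumed. The windows are ±2, ±3 and ±4 weeks for Visits 6, 7 and 8 (Protocol section 8).

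With weeks 12, 26 and 52:

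- Visit 6 to Visit 7: 26 − 12 = 14 weeks; shortest (26 − 3) − (12 + 2) = 9; longest (26 + 3) − (12 − 2) = 19.
- Visit 6 to Visit 8: 52 − 12 = 40 weeks; shortest (52 − 4) − (12 + 2) = 34; longest (52 + 4) − (12 − 2) = 46.

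Other conventions change this little:

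| Assumed weeks for Visits 6, 7, 8 | Visit 6 to 7 (range) | Visit 6 to 8 (range) |
|---|---|---|
| 12, 26, 52 | 14 (9 to 19) | 40 (34 to 46) |
| 13, 26, 52 | 13 (8 to 18) | 39 (33 to 45) |
| 12, 24, 48 | 12 (7 to 17) | 36 (30 to 42) |

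The newest summarised audiogram at the 6-month lock is thus nominally 12 to 14 weeks older than the visit that the lock is meant to describe.

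**4. What else would show Visit 7**

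- *Adverse events.* Protocol 7.2.4 makes a shift from the pre-operative baseline of more than 15 dB at any frequency an adverse event. SAP 4.11.2 summarises adverse events by CTCAE term as counts. It plans no threshold values and no breakdown by frequency or visit, and shifts of 15 dB or less do not enter.
- *BC Direct.* The SAP analyses it at 6 months (3.2.2, 4.10.2) at the same nine frequencies. It is an unmasked threshold obtained through the sound processor (Protocol 5.11) and is classed as efficacy. Under SAP 4.2, efficacy is not evaluated at the 6-month lock.
- *General rules.* The presentation by visit in SAP 4.1 is for efficacy variables. Figures are left for later (7.2) and listings are settled outside the SAP (7.3), so neither pre-specifies a Visit 7 summary.

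**The case against.** The strongest reply is that little is lost. The protocol's section on safety analyses (10.6) covers the implant site, adverse events and device deficiency, and specifies no audiogram analysis. On that reading the SAP contradicts no stated analysis, and its section 6 is not shown to be false. The Visit 7 measurement is still scheduled, so the data should exist. The event that the protocol itself treats as clinically significant, a shift above 15 dB, reaches the 6-month report as an adverse event. BC Direct also gives bone-conduction thresholds at 6 months. What remains is a missing column of descriptive statistics in two tables. In addition, SAP 1.1 speaks of post-operative thresholds without limit, and the body of the SAP flow chart is not in the text available here. It may mark Visit 7.

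Much of this stands, and it limits the point. The SAP narrows the time points of a protocol outcome measure; it does not alter a stated protocol analysis. The table list alone would be weak evidence, because it is not exhaustive. The point rests on SAP 3.3.4 and 4.11.4.

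The reply does not remove the mismatch. Protocol 10.10 promises an SAP that specifies analyses for every variable and time point, and the audiogram is a listed safety variable with a scheduled 6-month measurement. Adverse-event counts do not show the distribution of thresholds. BC Direct is a different, unmasked measurement and is not reported at the 6-month lock. If the SAP flow chart does mark Visit 7, the SAP disagrees with itself, and the analysis text still leaves the visit out.

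**Conclusion.** The concern holds. One of three scheduled post-operative bone-conduction audiograms, the 6-month one, has no planned summary in the SAP, although 6 months is the primary safety time point in both documents. The variable definition and the analysis text both omit it, the table titles agree, and no reason is given. It is therefore more than a slip in one sentence.

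The consequence is limited. As written, the 6-month safety analysis would summarise audiograms no later than Visit 6, nominally 12 to 14 weeks before Visit 7 depending on how months are converted to weeks. The 12-month tables would not fill the gap. No hypothesis, decision threshold or confirmatory claim depends on Visit 7, and shifts above 15 dB would still be counted as adverse events. This should be corrected before the 6-month lock, but it does not threaten the trial's main conclusions. The finding assumes that no separate document already plans the Visit 7 summary.

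**What to change.** Add Visit 7 (6 months) to SAP 3.3.4, to both sentences of SAP 4.11.4, and to bone-conduction Tables 14.1.5.2 and 14.1.5.4. State that these tables form part of the 6-month primary safety analysis. If the omission is intended, say so in SAP section 6 and give the reason. Check the SAP flow chart at the same time so that it agrees with the text.

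The cost is a few words in the SAP and added columns in two tables. No new data collection is required, because the protocol already schedules the measurement.

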| To collect information about the magnet choice and daily use of sound processor | 
 • Daily usage time • Comfort • Softpad use • Choice of magnet strength |
| To measure hearing performance preoperatively with a Baha BP110 Power sound processor on a Baha Softband | 
 • Thresholds audiometry, free-field [PTA4, Mean of 0.5, 1, 2 and 4 kHz]. • Thresholds audiometry, free-field [0.25, 0.5, 0.75, 1.0, 1.5, 2.0, 3.0, 4.0, 6.0 and 8.0 kHz]. • Speech in quiet [% correctly perceived words at 50dB, 65dB and 80dB SPL]. • Adaptive speech in noise [speech-to-noise ratio, 50% speech understanding]. • BC Direct [0.25, 0.5, 0.75, 1.0, 1.5, 2.0, 3.0, 4.0 and 6.0 kHz]. |
| Tertiary Objective | Outcome measure(s) |
| To measure hearing performance preoperatively with a current hearing aid (if used by the patient). | 
 • Adaptive speech in noise [speech-to-noise ratio, 50% speech understanding]. |

| Safety objective(s) | Outcome measure(s) |
|---|---|
| Primary safety analysis at 6 months. | |
| Implant site evaluations | Numbness |
| Adverse Events and concomitant medication/treatment | Information will be collected from Visit 2 and onwards. |
| Device deficiency | Information will be collected from Visit 2 and onwards. |
| Audiogram | Bone conduction thresholds preoperative and postoperative (3, 6, and 12 months) |

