5.5 Audiogram

Unaided audiometric threshold measures (including both air- and bone conduction thresholds) should demonstrate that the subject has a conductive, mixed hearing loss or single-sided sensorineural deafness and meets the audiological inclusion criteria.

An existing audiogram may be used as long as it has been completed during the last six months, and contains all the required relevant frequencies (250, 500, 750, 1000, 1500, 2000, 3000, 4000, 6000 and 8000Hz). The subject's pre-operative Pure Tone Average PTA4 (mean of 500, 1000, 2000 and 4000Hz) should be computed and recorded to ensure the subject meets the inclusion criteria.

If an audiogram is older than 6 months or does not contain the required frequencies, a new will be performed at Visit 1. Frequencies required for air conduction thresholds are 250, 500, 750, 1000, 1500, 2000, 3000, 4000, 6000 and 8000Hz. Bone conduction thresholds are 250, 500, 750, 1000, 1500, 2000, 3000, 4000 and 6000Hz. Contralateral masking should be used if needed, and according to local practice. The hearing care professional shall always record the unmasked threshold and record the masked if applicable.

Audiograms for bone conduction thresholds will also be performed at Visits 6, 7, and visit 8 to monitor hearing thresholds postoperatively.

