7.2.4 Clinically significant threshold shifts

Shifts in threshold, relative to the preoperative baseline, will be reported as an adverse event (AE) when a shift at any frequency exceeds 15 dB HL.

7.2.5 Handling and reporting of AESIs, SAEs and device deficiency that could have led to a SAE

An investigator should report within 24 hours, after being aware of the event, an AESI, SAE or a device deficiency that could have led to a SAE. The report shall be sent as an email attachment to the safety inbox or faxed to Cochlear Bone Anchored Solutions AB. Contact information is available on the SAE form.

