If the first analysis is significant the probability mass 0.025 will go to the second analysis. If the second analysis is also significant the probability mass 0.025 will go to the third analysis and so on. When the first non-significant analysis is reached this and all analyses thereafter will be non-confirmative while the previous analyses will be confirmative. If the first analysis is non-significant no analysis will be confirmative.

STATISTISKA KONSULTGRUPPEN		Statistical Analysis Plan	
Protocol: Clinical performance of a new implant system for bone conduction hearing		Protocol No: CBAS5539	
		Version: 1.0	Page 14 of 22

The hierarchical testing will be made for each arm separately (SSD and Mixed/Conductive) and not totally.

We plan to analyse the similarity of the primary efficacy results among sites using non-parametric one way analyses of variance (Kruskal-Wallis test) of the difference between Unaided and ATB at 3 months. This will only be made totally and not by SSD and Mixed conductive.

Imputation of missing values will be performed for all efficacy variables. No imputation of baseline values or baseline carry forward will be made. Imputations will be made according to the following rules:

1. If a value is missing at the end of a patient, last observation will be carried forward.
2. If a missing value is occurring between two time points with values, an interpolation will be made for continuous variables and for categorical variables the value from the previous visit will be carried forward.

The distribution of continuous variables as well as change in continuous variables will be given as n, mean, SD, SEM, Median, Min and Max and the distribution of dichotomous and categorical variables will be given as number and percentages. One sided 97.5% CI will be presented where applicable.

Numbness, Adverse Events, Device deficiencies, Comfort, Usage, Surgical variables, Demographics, Baseline, Questions, Magnet strength variables will only be analysed descriptively.

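### SAP 4.11.4 presents bone-conduction thresholds by frequency, arm and visit but does not derive from them how many subjects exceeded the protocol's 15 dB shift criterion, so those cases are counted only if reported as adverse events

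*SAP*

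**What the plan says.** The audiogram is a listed safety variable (Protocol section 10.2.3). Protocol section 4.3 specifies it as "Bone conduction thresholds preoperative and postoperative (3, 6, and 12 months"), and Protocol section 5.5 gives the purpose of the postoperative measurements: "to monitor hearing thresholds postoperatively".

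Protocol section 7.2.4 sets an individual criterion. Shifts, "relative to the preoperative baseline, will be reported as an adverse event (AE"), count "when a shift at any frequency exceeds 15 dB HL".

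Protocol section 10.6 describes analyses of numbness, adverse events and device deficiency, and none of the audiogram. The analysis is therefore left to SAP section 4.11.4, where thresholds at each frequency on the test side, "by SSD and Conductive/Mixed patients will be presented at visit 1, 6 and 8". The bone-conduction tables are 14.1.5.2, titled "Audiogram (bone) at visit 1, 6 and 8 - SSD patients (Safety Population"), and 14.1.5.4, its counterpart for conductive patients.

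Two other SAP provisions bear on the point. Section 4.11.2 states: "Summaries by CTCAE term presenting n (%) of AEs and n (%) of subjects with at least one AE will be provided for" all AEs, SAEs, ADEs, SADEs and AESIs. Section 4.1 states: "The distribution of continuous variables as well as change in continuous variables will be given as n, mean, SD, SEM, Median, Min and Max".

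**The concern.** The protocol's criterion belongs to a subject: did this person's threshold move by more than 15 dB from his or her own baseline at any of the tested frequencies? The planned audiogram output belongs to a group: the thresholds at one frequency, in one arm, at one visit. The first cannot be recovered from the second.

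For an implant fixed to the skull, a natural audiometric safety figure is the number of subjects who met the protocol's own criterion, at which visit, and whether the shift was still there at the next one. If harm fell on a few subjects, group means would move little. By-visit summaries also compare partly different subjects once someone leaves the study, because the imputation rule in SAP section 4.1 covers efficacy variables only. At stake is whether the report can give that figure from measured data, or must rely on what was reported as adverse events.

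**Working it through.** There is no stated figure behind the audiogram analysis to reproduce. The check is a comparison of outputs, followed by some illustrative arithmetic.

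**1. What each planned output can show**

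| Output | Unit | Shows subjects above 15 dB at any frequency? |
|---|---|---|
| SAP 4.11.4; Tables 14.1.5.2, 14.1.5.4 | frequency × arm × visit | No; neither change nor a shift category is named |
| SAP 4.1 summary of change, if applied to the audiogram | frequency × visit | No; the maximum shows that at least one subject crossed at that frequency, and nine separate maxima do not give the number of subjects |
| SAP 4.11.2 adverse-event tables | subjects per CTCAE term | Only if the shift was reported, and only if the term contains nothing else |

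Section 4.11.4 does not mention change. The SAP does name it elsewhere when it is meant, for example for numbness (4.11.1) and for the fitting-software comparison (4.12). Whether the section 4.1 rule on change reaches the audiogram is therefore open.

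**2. What the adverse-event route requires**

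Protocol section 6.1 gives nine bone-conduction frequencies at three postoperative visits. Comparisons per subject: 9 × 3 = 27. For 50 subjects: 27 × 50 = 1,350. Neither document says who makes these comparisons, and neither plans to derive the shifts centrally or to reconcile them with the reported events.

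**3. Effect of individual losses on a by-visit mean**

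Movement of the mean = (subjects affected × loss) / n, all others unchanged. The documents give 50 subjects in total and at least 13 per arm; 25 per arm is an assumption.

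- Three losses of 20 dB, n = 25: 3 × 20 / 25 = 2.4 dB
- One loss of 40 dB, n = 25: 1 × 40 / 25 = 1.6 dB
- One loss of 20 dB, n = 13: 20 / 13 = 1.5 dB
- One loss of 20 dB, n = 50: 20 / 50 = 0.4 dB

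If thresholds vary between subjects with an SD of 10 to 20 dB (assumption), the standard error of one by-visit mean at n = 25 is SD/√25 = 2 to 4 dB. This applies to an unpaired by-visit mean, not to the mean within-subject change. The first pattern, reported as a count, would read 3/25 = 12%, exact 95% CI 2.5% to 31.2%.

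**4. How often an unchanged ear would cross 15 dB**

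Assume test-retest differences that are normal, independent across nine frequencies, with SD 5 to 7 dB. None of this is in the documents. Chance of an apparent worsening above 15 dB at one frequency: p = 1 − Φ(15/SD). At any of nine: 1 − (1 − p)^9.

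- SD 5: p = 0.00135; any of nine = 1.2%
- SD 6: p = 0.0062; any of nine = 5.5%
- SD 7: p = 0.0161; any of nine = 13.6%

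A derived count would thus contain some measurement variation, and the per-frequency rows are needed to read it.

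**The case against.** The strongest reply is that the plan already has an individual-level route. Protocol 7.2.4 makes each shift above 15 dB an adverse event, and SAP 4.11.2 counts subjects with adverse events. SAP 4.1 adds minimum and maximum, so a 40 dB loss would be visible as a maximum change if change is tabulated. Dilution of a mean hides a loss only if the mean is the only output, and it is not. This stands. A reader might infer that individual hearing losses are averaged out of the report, or that the plan has no means of stating them; the documents do not support either reading.

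It can also be said that the weakness of the adverse-event route is partly unknown. Data validation is left to a data management plan that is not among the documents (Protocol 12.2.3). Protocol 10.6.2 foresees tables per predefined adverse event, and a threshold shift may be one of these. Protocol 10.4 says in general terms that all tables will be produced by arm and pooled. SAP 7.3 leaves listings to be decided elsewhere, and these could show persistence or recovery. All of this is fair, but it shows only that the figure might be produced. SAP 4.11.2 names CTCAE terms alone, its adverse-event tables are listed neither by visit nor by arm, and nothing in either document ties them to the recorded thresholds.

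Finally, test-retest variation across nine frequencies will produce some crossings without harm. That is a reason to treat the count as descriptive, not a reason to omit it; a site applying the same criterion would meet the same variation.

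**Conclusion.** The point holds in a limited form. The SAP does not derive from the recorded bone-conduction thresholds the number of subjects who met the criterion of Protocol 7.2.4. Reported adverse events are the only planned count, and that count depends on reporting, is not planned by visit, and need not separate these cases from others under the same term. Minimum and maximum show that a large shift occurred at a frequency, not how many subjects crossed at any frequency.

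The gap concerns descriptive safety reporting. No endpoint, alpha, sample size or safety decision rule depends on it. The dilution figures (0.4 to 2.4 dB) illustrate by-visit means only and rest on assumed numbers of affected subjects and, for the 2.4 and 1.6 dB figures, on an assumed 25 per arm. A change is still worth making, because a paired summary and a derived count answer the protocol's own question from data already in hand. The visits at which the SAP presents the audiogram are a separate matter.

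**What to change.** In SAP section 4.11.4 and Tables 14.1.5.2 and 14.1.5.4, for each postoperative visit with bone-conduction data, add:

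1. the within-subject change from the preoperative threshold at each frequency, with the summary statistics of SAP section 4.1;
2. n (%) of subjects, with exact 95% CI, whose threshold worsened by more than the figure in Protocol 7.2.4, at any frequency and at each frequency, by arm and in total.

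State in the SAP that the count refers to worsening, since Protocol 7.2.4 speaks of a shift without direction. State also which thresholds are used, comparing masked with masked and unmasked with unmasked, since both may be recorded. Reconcile the derived count with the threshold-shift adverse events before database lock, and describe the count as descriptive.

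The cost is SAP wording and some rows in two tables; no new measurements are needed. There are two small downsides. The count may raise queries about shifts that were not reported as adverse events, and some single-frequency crossings will be test-retest variation.
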